16.33 Objective Response

Objective Response (unconfirmed) is defined as achieving a complete or partial response while on treatment. The objective response rate (ORR) will be calculated as the proportion of evaluable patients who achieve objective response. Disease status will be assessed using RECISTsv1.1 criteria. Evaluable patients are defined as those who are eligible, consented, and received any protocol treatment. Confidence intervals for the true success proportion will be calculated according to the approach of Clopper and Pearson.

16.34 Duration of Response

Duration of response (DoR) is defined for all evaluable patients who have achieved an objective response as the date at which the patient's earliest best objective status is first noted to be either a CR or PR to the earliest date progression is documented, or death if no prior evidence of disease progression. The distribution of DoR will be estimated using the method of Kaplan-Meier. The median DoR and corresponding 95% confidence interval will be reported.

16.354 Adverse Events

All patients who have initiated treatment will be considered evaluable for adverse event analyses. Adverse events by patient will be summarized by frequencies and severity using CTCAE version 5.0. The proportion of patients who experience at least one grade 3+ adverse event (regardless of attribution) will be reported.

16.4 Correlative Research

Genomic analyses will be performed on mandatory blood samples collected from patients at the start of therapy, every 8 weeks, and at progression. An optional biopsy will be performed at the time of disease progression. Additionally, all patients who consent to the study also provide consent for the collection of previously collected paraffin embedded tissue. Analysis methods may include RNASeq, flow sorting enabled whole exome sequencing, and whole methylome analysis at multiple timepoints. These analyses would be performed in the laboratory of [REDACTED] at Mayo Clinic Arizona (see Section 14.0).

Specific goals of the correlative research include the following:

- 16.41 To determine the prevalence of mutations including those targeting DNA repair pathways.
- 16.42 To identify mutational signatures associated with pathogenic process in advanced biliary tract cancer samples.
- 16.43 To correlate the presence of mutations and mutational signatures linked to mutations in DNA repair/HRR with clinical responses.
- 16.44 To evaluate putative biomarkers related to: (a) *de novo* sensitivity and (b) tumor evolution and resistance, to PARP inhibition in BTC.

16.5 Data & Safety Monitoring

16.51 Review

The study chair(s) and the study statistician will review the study at least twice a year to identify accrual, adverse event, and any endpoint problems that might be developing. The Mayo Clinic Cancer Center

(MCCC) Data Safety Monitoring Board (DSMB) is responsible for reviewing accrual and safety data for this trial at least twice a year, based on reports provided by the MCCC Statistical Office.

16.52 Adverse Event Stopping Rules

Olaparib is an approved therapy in other diseases, the safety profile is well established, and the therapy is considered safe.^{27, 33-35}

The stopping rules specified below are based on the knowledge available at study development. We note that the Adverse Event Stopping Rule may be adjusted in the event of either (1) the study re-opening to accrual or (2) at any time during the conduct of the trial and in consideration of newly acquired information regarding the adverse event profile of the treatment(s) under investigation. The study team may choose to suspend accrual because of unexpected adverse event profiles that have not crossed the specified rule below.

Accrual will be temporarily suspended to this study if at any time we observe events considered to be clinically relevant and at least possibly related to study treatment (i.e., an adverse event with attribute specified as “possible”, “probable”, or “definite”) that satisfy the following:

- If 2 or more patients in the first 20 treated patients (or 10% of all patients after 20 are accrued) experience a grade 3+ non-hematologic adverse event.

We note that we will review Grade 4 and 5 adverse events deemed “unrelated” or “unlikely to be related”, to verify their attribution and to monitor the emergence of a previously unrecognized treatment-related adverse event.

16.55 CT.gov Reporting

Expected durations and timelines for certain events (e.g. accrual) and endpoints for CT.gov reporting purposes can be found in sections 16.24 and 16.21 respectively.

17.0 Pathology Considerations/Tissue Biospecimens

17.1 Tissue Biospecimen Submission

17.11 Summary Table of Tissue Biospecimens for This Protocol

Type of tissue biospecimen to submit	Mandatory	When to submit	Reason for submission (background/methodology section)
Formalin-fixed paraffin-embedded (FFPE) tissue blocks with corresponding H&E	Mandatory	≤28 days after registration	Correlative studies (Section 17.5)

Fresh Frozen Tumor Tissue (2-3) cores	Optional	EOT	Correlative studies (Section 17.5)
Formalin-Fixed paraffin embedded (FFPE) tissue blocks with corresponding H&E	Optional	EOT ¹	Correlative Studies (Section 17.5)

¹ Submit if fresh frozen is not obtained.

Archival tissue will be collected for correlative studies and to confirm HRD status. Patients may initiate study treatment prior to the receipt of the archival tissue. Additional tumor and unaffected liver tissue may be collected at the time of standard of care biopsy for diagnostic confirmation if a clear histologic diagnosis is unable to be made with archival tissue. At end of treatment, if a biopsy for routine clinical molecular profiling (using commercial assays such as Foundation One or Caris) is done, again, additional tumor and liver tissue may be obtained. For both time points (at time of standard of care diagnostic confirmation and at end of treatment when performing routine clinical molecular profiling), additional preferably fresh frozen 2-3 cores of tumor tissue using an 18 gauge needle should be collected. Tissue will be flash frozen and stored in a -80 degree freezer or shipped on dry ice to the [REDACTED] laboratory. If fresh frozen tissue is not available, archival tissue may be used. Collection of additional tissue at time of standard of care biopsies at screening and end of treatment likewise is optional.

17.2 Paraffin Embedded Tissue Blocks/Slides

- 17.21 Submit one formalin fixed paraffin-embedded (FFPE) tumor tissue block with largest amount of invasive tumor (at least 1 cm of tumor for cases of surgical resection) (from either primary or metastatic site). **A corresponding H&E slide for each submitted block must be provided. The H&E slide for each block should be reviewed by the institution's pathologist to assess tissue quality prior to submission.**
- 17.22 The FFPE tissue block is preferred; however, **if an institution is unable to provide a tissue block**, If not available in this format, up to 3 unstained, standard 50 micron scrolls/curls can be sent. **Label the tubes with ACCRU patient ID number, accession number, and order of sections (4-5 microns).** H&E stain the first and last slide (i.e., slides labeled 1, 3, etc.). The H&E slides should be reviewed by the institution's pathologist to assess tissue quality prior to submission. **Do not bake or place covers slips on the slides.**
- 17.23 The following materials below are mandatory (unless indicated otherwise) and required for shipment:
- Paraffin embedded tissue blocks with corresponding H&E slide (OR 3 unstained slides with corresponding H&E(s)).
 - Specimen Submission: Tissue form
 - Surgical Pathology Report
 - Operative Report (*optional*)
 - **Note: Please include the ACCRU patient ID number on all materials listed above.**

- 17.24 The block/slides must be appropriately packed to prevent damage (e.g., slides should be placed in appropriate slide container) and placed in an individual plastic bag. Label the bag with the protocol number, ACCRU patient ID number, and patient initials. During warm weather months, paraffin blocks should be shipped using a refrigerant pack to avoid heat that may melt paraffin and damage blocks.
- 17.25 FFPE tissue specimens must be shipped ≤ 28 days after registration.
- 17.26 Verify that the appropriate sections of the Specimen Submission: Tissue form are completed and filled in correctly. Enter information from the Specimen Submission: Tissue form into the remote data entry system on the same day the specimen is submitted (see Forms Packet).
- 17.27 Ship all block/slide tissue specimens and accompanying materials to the Mayo Biobank:

- 17.28 The block and appropriate paperwork will be returned to the Mayo Clinic, [REDACTED]

- 17.29 When an appropriate request is submitted, the Mayo Biobank will forward the block/slides to [REDACTED] Mayo Clinic Arizona, for processing as outlined in Section 17.5.

17.3 Frozen Tumor tissue:

Biopsies (25-50 mgs) will be thawed then minced in the presence of NST buffer and DAPI according to published protocols^{36,37}. Nuclei from each sample will be disaggregated then filtered through a 40 μ m mesh prior to flow sorting with an Influx cytometer (Becton-Dickinson, San Jose, CA) with ultraviolet excitation and DAPI emission collected at >450 nm. DNA content and cell cycle will be analyzed using the software program MultiCycle (Phoenix Flow Systems, San Diego, CA).

17.4 Study Methodology and Storage Information

- 17.41 Submitted tissue samples will be analyzed as follows:

We will focus on whole exome methods for these FFPE samples. As part of this study we will screen each sorted sample with our established quality control (QC) metrics. These will include tumor content, cellular debris, DNA yield, and fragment sizes prior to library preparation. Based on our experience with metastatic biopsy FFPE samples from clinical trials we anticipate that 10-12 cases

will be suitable for our whole exome analyses.

17.42 Next Generation Sequencing:

17.421 DNA templates

The DNA from each sorted tumor and a patient matched normal sample will be extracted with our standard protocols. Normal DNA will be extracted from either blood samples or the non-tumor fraction from sorted tissues. All DNAs will be assessed with our QC assays and metrics.

17.422 Whole genome sequencing of sorted frozen samples

A 1ug aliquot of high molecular weight DNA from each tumor and normal sample of interest will be used for all whole genome sequencing. The quantity and quality of each sample will be assessed by standard QC metrics using a QuBit fluorometer prior to shipping to the Mayo Genome Facility (MGF) in Rochester.

17.423 Whole exome sequencing of sorted FFPE samples

For FFPE samples we will use ThruPLEX[®] DNA-seq Kit to prepare paired-end libraries for each sorted tumor population and matching normal sample of interest. We will use a minimum input of 10ng for all library preparations. Aliquots of each library will be QC'ed on a BioAnalyzer prior to shipment to the MGF. Subsequently, whole exon capture will be carried out with Agilent's SureSelect Human All Exon 71 MB v6 kit. Briefly 500 ng of the prepped library is incubated with whole exon biotinylated RNA capture baits supplied in the kit for 24 hours at 65 °C. The captured DNA:RNA hybrids are recovered using Dynabeads MyOne Streptavidin T1 (Dyna). The DNA is eluted from the beads and desalted using purified using Ampure XP beads (Agencourt). The purified capture products were then amplified using the SureSelect Post-Capture Indexing forward and Index PCR reverse primers (Agilent) for 12 cycles. Libraries were loaded onto paired end flow cells at concentrations of 4-5 pM to generate cluster densities of 600,000-800,000/mm² using the Illumina cBot and HiSeq Paired end cluster kit version 3. The flow cells are sequenced as 101 X 2 paired end reads on an Illumina HiSeq 2500 or 4000 using TruSeq SBS sequencing kit version 3 and HiSeq data collection version 1.4.8 software. Base-calling was performed using Illumina's RTA version 1.12.4.2.

17.43 Data Analysis:

17.431 Mutation calling

All secondary analyses will be done through the Mayo Clinic Bioinformatics Core (BIC). This will include filtering observed variants based on a series of criteria including NextProt Feature Strength, Maximum Population Allele Frequency, and inclusion in the Catalogue of Somatic Mutations in Cancer (COSMIC) database³⁸. The goal will be to prioritize those variants that likely disrupt protein function, identify mutations targeting known cancer related DNA repair genes and pathways, and filter out common polymorphisms reported in dbSNP and

other population based studies.

17.432 Mutational signature

We will work with Mayo Clinic bioinformaticians to extract mutational signatures from the next generation sequencing (NGS) data from each sample of interest. Of significant interest will be the presence of a HRD associated signature (Signature 3) that associates strongly with elevated numbers of large (longer than 3bp) insertions and deletions with overlapping microhomology at breakpoint junctions.

Instructions for shipment of samples to the analysis laboratory and shipping supplies will be provided by the Coordinating Center. All flow sorting of tissue samples, DNA extractions, and FFPE library preparations will be done in the [REDACTED] laboratory on the MCA Scottsdale campus.

- 17.44 At the completion of the study, any unused/remaining material will be stored in in [name] at Mayo Clinic Arizona for future research according to the patient consent permission (see Section 6.5). Potential future research may include immunohistochemistry (IHC) analyses to analyze predictive biomarkers, changes in expression pattern with therapy, and correlation with response and/or adverse events. When a protocol is developed, it will be presented for IRB review and approval.
- 17.45 Banking of tumor tissue, according to the patient consent permission (see Section 6.5), is for future research. As protocols are developed, they will be presented for ACCRU and IRB review and approval. (This collection is part of a general strategy of investigation for ACCRU melanoma studies).
- 17.46 The institutional pathologist will be notified by the Biospecimen Manager if the block may be depleted.
- 17.47 Blocks requested to accommodate individual patient management will be returned promptly upon request.

17.5 Return of Genetic Testing Research Results

No genetic specimens will be collected from tissue biospecimens for this study. If future genetic testing is being requested for stored tissue, patient reconsent is required.

18.0 Records and Data Collection Procedures

All data must be entered by Remote Data Entry (RDE) and completed by qualified and authorized personnel. Access the RAVE RDE system through the iMedidata portal at

[REDACTED] All data on the CRF must reflect the corresponding source document. Please refer to the ACCRU website for instructions [REDACTED]

18.1 Submission Timetable

Initial Material(s)

CRF	Active-Monitoring Phase (Compliance with Test Schedule Section 4.0)
Institutional Contacts	≤2 weeks after registration
On-Study	
On-Study: Prior Systemic Therapy ¹	
Adverse Event: Baseline	
RECIST Measurements: Baseline	
Laboratory Tests & Results: Baseline	
Supporting Documentation: Baseline ²	
Concomitant Medications	
Specimen Submission: Blood (Baseline) (see Section 14.0)	
Patient Status: Baseline	
OP and Path Reports (see Section 17.0) ²	
Specimen Submission: Tissue (Baseline) (see Section 17.0)	< 28 days after registration
Off Treatment	Submit ≤2 weeks after registration if withdrawal/refusal occurs prior to beginning protocol therapy
ACCRU Deviation Form ¹	Submit only if applicable during all phases of the study (initial, active and observation)

1. Submit only if applicable.
2. Upload via the Supporting Documentation: Baseline form. This is in addition to the pathology material requirements for tissue submission (Section 17.0). Tumor molecular profiling report demonstrating genetic aberrations that are associated with homologous recombinant repair pathway for eligibility.

Test Schedule Material(s)

CRF	Active-Monitoring Phase (Compliance with Test Schedule Section 4.0)	
	At each evaluation during treatment	At end of treatment
Treatment (Intervention)	X	X
Treatment (Intervention): Dose Modifications, Omissions and Delays ¹	X	
Adverse Events: Solicited	X	X
Adverse Events: Other ¹	X	X
RECIST Measurements ²	X	X
Supporting Documentation ²	X	X
Concomitant Medications	X	
Specimen Submission: Blood (see Section 14.0) ¹		
Specimen Submission: Tissue (see Section		

CRF	Active-Monitoring Phase (Compliance with Test Schedule Section 4.0)	
	At each evaluation during treatment	At end of treatment
17.0) ¹		
Patient Status: Treatment (Intervention)	X	X
Notice of New Primary ¹	X	X
Consent Withdrawal (choose appropriate form) ¹	X	X

 Consent Withdrawal: Specimen Only Consent Withdrawal: All Follow-Up 		
Off Treatment		X
ACCRU Deviation ¹	X	X

1. Submit only if applicable.
2. Upload documentation of response or progression on the Supporting Documentation form.
3. Patients are eligible to be confirmed lost to follow-up after 2_years of unsuccessful contact with the patient.

Follow-up Material(s)

CRF	Event Monitoring Phase¹				
	q. 3 months until PD	At PD	After PD q. 3 mos.	Death	New Primary
Patient Status: Survival and Disease Status Follow-Up/Event Monitoring	X ²	X ²	X	X	At each occurrence
Adverse Events: Late ³					X
Supporting Documentation ³					
Notice of New Primary ³					X
Consent Withdrawal (choose appropriate form) ³					X

 Consent Withdrawal: Specimen Only Consent Withdrawal: All Follow-Up 					
Lost to Follow-Up ³					
ACCRU Deviation Form ³	X ³	X ³	X ³	X ³	

1. If a patient is still alive 3 years after registration, no further follow-up is required.
2. Upload a copy of documentation of response or progression in RAVE on the Supporting Documentation Form.
3. Submit only if applicable.

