6.23 Correlative Research

Mandatory

A mandatory correlative research component is part of this study. The patient will be automatically registered onto this component (see Sections 3.0, 14.0 and 17.0).

Optional

An optional correlative research component is part of this study, there will be an option to select if the patient is to be registered onto this component (see Section 17.0).

- Patient has/has not given permission to give his/her tissue sample for research testing.

6.24 At the time of registration, the following will be recorded:

- Patient has/has not given permission to store and use his/her sample(s) for future research to learn about, prevent, or treat cancer.
- Patient has/has not given permission to store and use his/her sample(s) for future research to learn, prevent, or treat other health problems (for example: diabetes, Alzheimer's disease, or heart disease).
- Patient has/has not given permission for ACCRU to give his/her sample(s) to outside researchers.

6.25 Treatment cannot begin prior to registration and must begin ≤ 7 days after registration.

6.26 Pretreatment tests/procedures (see Section 4.0) must be completed within the guidelines specified on the test schedule.

6.27 All required baseline symptoms (see Section 10.5) must be documented and graded.

6.28 Treatment on this protocol must commence at an ACCRU institution under the supervision of a medical oncologist.

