10.0 Adverse Event (AE) Reporting and Monitoring

The site principal investigator is responsible for reporting any/all adverse events to the sponsor as described within the protocol. Refer to the adverse event and serious adverse event sections of the protocol for detailed information.

NOTE: Please see Appendix III for specific AE reporting regarding the study drug olaparib.

The sponsor/sponsor-investigator is responsible for notifying FDA and all participating investigators in a written safety report of any of the following:

- Any suspected adverse reaction that is both serious and unexpected.
- Any findings from laboratory animal or *in vitro* testing that suggest a significant risk for human subjects, including reports of mutagenicity, teratogenicity, or carcinogenicity.
- Any findings from epidemiological studies, pooled analysis of multiple studies, or clinical studies, whether or not conducted under an IND and whether or not conducted by the sponsor, that suggest a significant risk in humans exposed to the drug.
- Any clinically important increase in the rate of a serious suspected adverse reaction over the rate stated in the protocol or Investigator's Brochure (IB).

Definitions

Adverse Event

Any untoward medical occurrence associated with the use of a drug in humans, whether or not considered drug related.

Suspected Adverse Reaction

Any adverse event for which there is a reasonable possibility that the drug caused the adverse event.

Expedited Reporting

Events reported to sponsor within 24 hours, 5 days or 10 days of study team becoming aware of the event.

Routine Reporting

Events reported to sponsor via case report forms

Events of Interest

Events that would not typically be considered to meet the criteria for expedited reporting, but that for a specific protocol are being reported via expedited means in order to facilitate the review of safety data (may be requested by the FDA or the sponsor).

Adverse events after the 30 day follow up period

For Pharmacovigilance purposes and characterization, any SAE of MDS/AML or new primary malignancy occurring after the 30 day follow up period should be reported to AstraZeneca Patient Safety regardless of investigator's assessment of causality or knowledge of the treatment arm. Investigators will be asked during the regular follow up for overall survival if the patient has developed MDS/AML or a new primary malignancy and prompted to report any such cases.

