The designated AstraZeneca representative works with the Investigator to ensure that all relevant information is provided to the AstraZeneca Patient Safety data entry site within 1 or 5 calendar days for SAEs and within 30 days for all other pregnancies.

The same timelines apply when outcome information is available.

Paternal exposure

Male patients should refrain from fathering a child or donating sperm during the study and for 3 months following the last dose.

Pregnancy of the patient's partners is not considered to be an adverse event. However, the outcome of all pregnancies (spontaneous miscarriage, elective termination, ectopic pregnancy, normal birth or congenital abnormality) occurring from the date of the first dose until 3 months after the last dose should, if possible, be followed up and documented.

10.4 Expedited Adverse Event Reporting Requirements Studies using Commercial Agent(s) ONLY:

10.41 Expedited Reporting via the **MedWatch 3500A Form** for Adverse Events That Occur Within 30 Days¹ of the Last Dose of the Commercial Agent

FDA REPORTING REQUIREMENTS FOR SERIOUS ADVERSE EVENTS (21 CFR Part 312) NOTE: Investigators MUST immediately report to the sponsor ANY Serious Adverse Events, whether or not they are considered related to the investigational agent(s)/intervention (21 CFR 312.64) An adverse event is considered serious if it results in ANY of the following outcomes: 1) Death 2) A life-threatening adverse event 3) An adverse event that results in inpatient hospitalization or prolongation of existing hospitalization for ≥ 24 hours 4) A persistent or significant incapacity or substantial disruption of the ability to conduct normal life functions 5) A congenital anomaly/birth defect. 6) Important Medical Events (IME) that may not result in death, be life threatening, or require hospitalization may be considered serious when, based upon medical judgment, they may jeopardize the patient or subject and may require medical or surgical intervention to prevent one of the outcomes listed in this definition. (FDA, 21 CFR 312.32; ICH E2A and ICH E6).		
ALL SERIOUS adverse events that meet the above criteria MUST be immediately reported to the sponsor within the timeframes detailed in the table below.		
Hospitalization	Grade 1 and Grade 2 Timeframes	Grade 3-5 Timeframes
Resulting in Hospitalization ≥ 24 hrs	7 Calendar Days	24-Hour; 3 Calendar Days
Not resulting in Hospitalization ≥ 24 hrs	Not required	

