13.0 Treatment/Follow-up Decision at Evaluation of Patient

- 13.1 A patient is deemed *ineligible* if after registration, it is determined that at the time of registration, the patient did not satisfy each and every eligibility criteria for study entry.
- If the patient received treatment, the patient may continue treatment at the discretion of the physician as long as there are not safety concerns. The patient will continue in the Active Monitoring/Treatment phase of the study, as per section 4.0 of the protocol.
 - If the patient never received treatment, on-study material must be submitted.
- 13.2 A patient is deemed a *major violation*, if protocol requirements regarding treatment in cycle 1 of the initial therapy are severely violated that evaluability for primary end point is questionable. If the patient received treatment, the patient may continue treatment at the discretion of the physician as long as there are no safety concerns. The patient will continue in the Active Monitoring/Treatment phase of the study, as per section 4.0 of the protocol, and all data submission should continue per protocol. If the patient does not continue with treatment, the patient will go Off Treatment and be followed in Survival Follow-up
- 13.3 A patient is deemed a *cancel* if he/she is removed from the study for any reason before any study treatment is given. On-study material and the End of Active Treatment/Cancel Notification Form must be submitted. No further data submission is necessary.
- 13.4 Patients will continue treatment until progression or a maximum of 36 cycles, unacceptable adverse events, or patient refusal. Treatment will then be discontinued and the patient will go to event monitoring and be followed per Section 18.0.
- 13.5 Patients who are CR, PR, or SD will continue treatment per protocol or a maximum of 36 cycles.

- 13.6 Patients who develop PD while receiving therapy will go to the event-monitoring phase and will be followed for survival (i.e. event-monitoring phase) every 3 months (± 7 days) for 3 years after registration (per Section 18.0).
- 13.7 Patients who go off protocol treatment for reasons other than PD will go to the event-monitoring phase and be followed for survival and progression (i.e. event monitoring phase) every 3 months (± 7 days) for 3 years after registration (per Section 18.0).

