- 13.8 Event Monitoring is not part of the Active Monitoring phase of a study and is defined as the time period when the participant is no longer following the protocol test schedule. During Event Monitoring, the data collection schedule is dictated by the protocol but the visit schedule is determined by clinical practice at each participating site. During the Event Monitoring Phase of the study, the participant is being monitored for key study events such as progression, new primaries, and death. Event monitoring should occur every 3 months (± 7 days) until death or a maximum of 3 years following Registration. Phone or virtual visits are permitted during Event Monitoring.
- 13.9 The patient will be withdrawn from treatment if there are bone marrow findings consistent with myelodysplastic syndrome (MDS)/acute myeloid leukemia (AML). The patient will go to the event-monitoring phase per Section 13.7.

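### Event monitoring ends 3 years after registration whatever the date of last dose, so patients who complete 36 cycles may get one scheduled post-treatment prompt for MDS/AML and new primaries, or none

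*Combined protocol and SAP*

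**What the plan says.** **Treatment length.** A cycle is 28 days (Schema; Section 7.1). Section 13.4: "Patients will continue treatment until progression or a maximum of 36 cycles, unacceptable adverse events, or patient refusal". Section 6.25: "Treatment cannot begin prior to registration and must begin ≤ 7 days after registration".

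**End of follow-up.** Sections 13.6 and 13.7 send patients who stop treatment to 3-monthly event monitoring for 3 years after registration. Section 13.8 repeats the interval ("Event monitoring should occur every 3 months", with a 7-day window either way) and the limit ("until death or a maximum of 3 years following Registration"). It allows phone or virtual contacts. Footnote 1 in Section 18.1, attached to the Event Monitoring Phase heading, says "If a patient is still alive 3 years after registration, no further follow-up is required".

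**Late events.** Section 10.0 names MDS/AML and new primary malignancy as adverse events of special interest. It states that "any SAE of MDS/AML or new primary malignancy occurring after the 30 day follow up period should be reported to AstraZeneca", whatever the causality assessment, and that investigators will be asked about these events at the routine survival follow-up. Outside the exceptions it lists, it places no duty on sites to report new events actively once the 30-day period is over.

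**Contact after last dose.** Section 4.0 schedules one visit at 30 days. No section sets a minimum period of event monitoring counted from last dose.

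**The concern.** The protocol singles out two delayed events for attention after treatment and ties the active question about them to survival follow-up. That follow-up has a fixed end counted from registration, while the start of the post-treatment period moves with the length of treatment. The longer a patient takes olaparib, the less scheduled post-treatment follow-up remains, and at the treatment maximum almost none does.

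At stake is how the late safety data can be read. If no late MDS/AML or new primary is recorded among patients treated for 2 years or more, part of the reason could be that they were scarcely asked about it after stopping.

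**Working it through.** The documents state no figure for the remaining window, so there is none to reproduce. The check is calendar arithmetic.

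**Inputs.** Cycle of 28 days (Schema); maximum 36 cycles (13.4); first dose 0 to 7 days after registration (6.25); limit of 3 years from registration (13.8, 18.1), taken as 3 × 365.25 = 1095.75 days; contacts every 3 months (13.8), taken as 365.25 / 4 = 91.3 days, with 7 days either way.

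**Window after last dose.** Window = 1095.75 − 28 × cycles − start delay. If contacts are counted from end of treatment, the number that fit is the window divided by 91.3, rounded down.

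| Cycles completed | Days on treatment | Window, day-0 start | Window, day-7 start | Contacts that fit |
|---|---|---|---|---|
| 2 | 56 | 1040 | 1033 | 11 |
| 12 | 336 | 760 | 753 | 8 |
| 24 | 672 | 424 | 417 | 4 |
| 30 | 840 | 256 | 249 | 2 |
| 36 | 1008 | 88 | 81 | 0 |

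After 36 cycles the 30-day visit uses part of the window, leaving about 58 days (day-0 start) or 51 days (day-7 start).

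**Does a contact fall inside the limit after 36 cycles?** Sections 13.6 to 13.8 do not say where the 3-monthly interval starts, so both readings are shown.

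- *From end of treatment.* The first contact is due on day 1008 + 91.3 = 1099.3 (day-0 start) or 1106.3 (day-7 start), both after day 1095.75. Using the full 7-day early window gives day 1092.3 or 1099.3. One contact therefore fits only if it is made early and dosing began within about 1095.75 − 1092.3 = 3.4 days of registration.
- *From registration.* The contact at month 33 is due on day 11 × 91.3 = 1004, before last dose. The contact at month 36 is due on day 1095.75, which is the limit itself and 81 to 88 days after last dose. One contact fits.

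So the count is one or none.

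**Interruptions (assumption).** Section 8.0 allows repeated interruptions of up to 4 weeks, but the documents do not say whether these lengthen the calendar time of 36 cycles. If they do, 87.75 / 28 = 3.1 and 80.75 / 28 = 2.9. Four full interruptions (day-0 start) or three (day-7 start) would then leave no event-monitoring window when treatment stops.

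**How many patients (illustration).** The documents give no number. Assume a constant rate of progression and no other reason for stopping. Then 36 cycles are 1008 / 56 = 18 eight-week periods and 24 cycles are 12. Of 30 patients:

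| Progression-free per 8 weeks | Expected at 24 cycles | Expected at 36 cycles |
|---|---|---|
| 70% (design alternative, 16.2) | 30 × 0.7^12 = 0.4 | 30 × 0.7^18 = 0.05 |
| 80% | 30 × 0.8^12 = 2.1 | 30 × 0.8^18 = 0.5 |
| 90% | 30 × 0.9^12 = 8.5 | 30 × 0.9^18 = 4.5 |

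A subgroup with durable benefit would raise these counts; stopping for toxicity or refusal would lower them.

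**The case against.** The best defence is that long-treated patients are watched closely. On drug they have a visit, blood counts and adverse event assessment every cycle (Section 4.0). A new-primary form applies at each evaluation (18.1), and persistent cytopenia has its own work-up rules (8.2). Their total observation from registration is no shorter than anyone else's. Late cases also remain reportable with no stated end date (10.0), late MDS/AML incidence is not an endpoint, and few patients may be affected. All of this stands and limits the weight of the point. It does not restore the missing prompt: after 3 years nothing makes anyone ask.

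Several stronger readings are tempting, and the documents do not support them:

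- *Follow-up stops while a patient is still on olaparib.* Footnote 1 belongs to the Event Monitoring heading, and Section 13.8 separates that phase from active monitoring. A patient on drug stays under Section 4.0, including the 30-day visit. Section 10.0 also requires continued SAE collection if treatment goes on after study completion.
- *The 7-day visit window lengthens every cycle.* The cycle is defined as 28 days. Treating the window as added treatment time needs all 36 visits to run late and the delays to accumulate.
- *The 1% to 10% band for MDS in Section 15.17 gives the number of missed cases.* That is a general toxicity band for the drug. The gap concerns only cases that arise after the limit in patients treated for a long time.
- *The partner-pregnancy follow-up is cut off.* Section 10.334 covers pregnancies "occurring from the date of the first dose until 3 months after the last dose should, if possible, be followed up and documented". Three months is about 91 days against 81 to 88, so the overrun is roughly 4 to 11 days. The duty is stated separately and not tied to event monitoring.

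**Conclusion.** The point holds for scheduled follow-up after treatment. Because the limit is counted from registration, the post-treatment window falls from about 1040 days after 2 cycles to 81 to 88 days after 36. At the maximum, the active question about MDS/AML and new primaries has one scheduled contact or none.

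This rests on 28-day cycles, a start within 7 days of registration and no added calendar time for interruptions. The choice between one and none depends on a starting point for the 3-monthly interval that the protocol leaves open.

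A reader might infer that the most exposed patients are observed least overall. They are not: only their off-drug period is short. The number reaching 24 to 36 cycles is not given and is probably small, and the primary endpoint at about 8 weeks is unaffected. This is a worthwhile low-cost improvement with a small expected gain, and no threat to the trial's main conclusion.

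**What to change.** In Sections 13.6, 13.7 and 13.8 and in footnote 1 of Section 18.1, end event monitoring at the later of 3 years after registration or a fixed interval after the last dose of olaparib. Three details complete it:

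- Make the interval long enough to guarantee at least one 3-monthly contact. With the 7-day window that means at least 91.3 + 7 = 98 days.
- State whether the 3-monthly interval counts from registration or from end of treatment.
- Say in Section 13.8 that each contact asks about survival, MDS/AML and new primary malignancy.

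The length is for the sponsor to set. Twelve months is one option and has no source in the documents. It would give 365.25 / 91.3 = 4 contacts after last dose. With a day-0 start it would matter only when last dose falls after day 1095.75 − 365.25 = 730.5, that is, beyond about 26 cycles.

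The cost is an amendment and a few extra phone or virtual contacts, which Section 13.8 already permits. Final database closure could also be later: with 12 months, follow-up of a patient completing 36 uninterrupted cycles from a day-0 start would end on day 1008 + 365.25 = 1373, about 277 days after the present limit. The primary analysis does not change.
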